1 PROTOCOL SUMMARY

1.1 Synopsis

Protocol Title	Evaluating the efficacy and comfort of the PureWick™ male external catheter against a comparator in Healthy Volunteers	
Short Title	MECCE (Male External Catheters' Comparison of Comfort & Efficacy)	
Rationale	The purpose of this study is to provide clinical evidence to compare the effectiveness and comfort of PureWick™ Male against a comparator for non-invasive urine output management in patients with varying male anatomy.	
Objectives and Endpoints	Objective(s)	Endpoint(s)
	Primary 
 To assess the performance of the PureWick™ Male (System) against an established comparator (Stryker/ Sage PrimoFit™) 	Primary 
 Capture rate following void (captured as % of urine captured by device and collected in canister, measured by weight)

Protocol Title	Evaluating the efficacy and comfort of the PureWick™ male external catheter against a comparator in Healthy Volunteers	
	
Secondary Objective (with Hypothesis Test):
 
 • To assess the performance of the PureWick™ Male (System) in patients that are unable to use traditional sheath style condom catheters. 
Secondary Objective (without Hypothesis test):
 
 • To assess participant comfort after using the MEC • To assess ease of use by HCP in placing the MEC 	
Secondary
 
 • Capture rate following void (captured as % of urine captured by device and collected in canister, measured by weight). • Overall Comfort score on a 5-point Likert scale (brief questionnaire) • Ease of use score on a 5-point Likert scale (brief questionnaire)
Design and Overview	This is a Prospective, Randomized, Crossover, Single-blind, Single Center Healthy Volunteer Study conducted over 1 day, with 2 voids using the PW Male external catheter vs. comparator Sage PrimoFit™. This study is designed to assess the performance, comfort, and ease of use of the PW Male external catheter as compared to the comparator product.	

Protocol Number: UCC-23AC022

CONFIDENTIAL

Version:1.0

Date: 16May2023

[figure not shown]
Protocol Title	Evaluating the efficacy and comfort of the PureWick™ male external catheter against a comparator in Healthy Volunteers
Study Device	
Test product(s): BD PureWick™ Male (PWM030)
 
The PureWick™ Male External Catheter (MEC) is intended for non-invasive urine output management in male patients. The PureWick™ Male External Catheter is a commercially available device which is Class I, 510(K) exempt.
 
Reference/Comparator product(s): Sage PrimoFit™ (5404)
 
The Sage PrimoFit™ is a commercially available device which is Class I, 510(K) exempt.
 
Ancillary Product(s):
 
 • Standard suction tubing and cannister • BBS Revolution: Bladder Scanner + Display (PD0100002) • Absorbent under-pads • Commercially available scales • Clippers/trimmers • Wipes/towels for peri-care • Turning wedge (45-degree foam wedge) • PPE

Protocol Title	Evaluating the efficacy and comfort of the PureWick™ male external catheter against a comparator in Healthy Volunteers
Participants	
Adult male healthy volunteers with a target of 50% of subjects in each of the following cohorts:
 
 ○ Cohort A: Non morbidly obese men: BMI <40 ○ Cohort B: Morbidly Obese men: BMI ≥40 ○ 
Inclusion Criteria:
 
 ● Adult Male Patients ≥18 years old ● Male anatomy at time of enrollment ● Ability to speak and understand English ● Willing to comply with all study procedures in this protocol ● Able to independently void urine ● Provision of signed and dated informed consent form 
Exclusion Criteria:
 
 ● Urinary incontinence which does not allow the subject to spontaneously void ● Frequent episodes of bowel incontinence ● Has Urinary Retention ● Has any irritation, wound, open lesion, at the application site, on the genitalia, perineum, or sacrum ● Recent surgery of the external urogenital tract, penis, or pubic area ● Not able to comply with study procedures independently without required assistance ● Any other condition that, in the opinion of the investigator, would preclude them from participating in the study

Intervention(s)/Procedure(s)	
Prior to arrival, participants will be instructed to consume fluids and to come to the test site with a full bladder. Upon arrival at the test site, participants will be consented and screened against inclusion/exclusion criteria. Those meeting eligibility criteria will be assigned a treatment order. Participants will be divided into two cohorts.
 
Cohort A: Non morbidly obese men: BMI <40
 
Cohort B: Morbidly obese men: BMI ≥40
 
Participants will be placed in the test area, instructed to undress, and put on a gown. The Health Care Professional (HCP) will complete a visual assessment of the participant's pubic/ genital region to ensure that the participant is trimmed and assess the anatomy. Trimmers can be provided if the participant did not arrive to the site trimmed. The HCP will then assess for a buried penis and/or anatomical compatibility with traditional sheath style condom catheters for each participant. "A buried penis refers to a normal-sized phallus encompassed by either skin, subcutaneous tissue, and/or fat in the prepubic area" causing a reduced visible and/or functional length of the phallus.¹¹
 
Void 1:
 
The bed in the test area will be set with a pre-weighed absorbent pad and a pre-weighed urine collection canister (with the lid). Once the participant feels the need to void, the Health Care Professional (HCP) will place either the PureWick™ MEC (Device A) or the Sage PrimoFit™ (Device B) (depending on randomized treatment order) according to the device instructions for use (IFU) and confirm the correct placement prior to the voiding episode. The participant will be placed in a semi-fowler position (head of bed elevated approximately 30 degrees) in a hospital bed and turned to one side using a turning wedge prior to the voiding episode. Participants will be monitored for approximately 2 hours from the time of the device application, through one void. (The skin needs to be assessed at least every two hours while wearing a MEC.) After the void, the pre-weighed absorbent pad and urine collection canister will be weighed (with the lid), and weights documented in the source. The Pure Wick MEC or Sage PrimoFit™ will be removed by the HCP. After removal, the HCP will note any signs of irritation/injury in the perineal area. Any unresolved erythema (redness), erythema (swelling), bleeding, injury, or rash should be recorded as an Adverse Event.

------------------------------	--

Protocol Title	Evaluating the efficacy and comfort of the PureWick™ male external catheter against a comparator in Healthy Volunteers
	
The participant will be asked to complete a brief survey to assess device comfort immediately after the completed void.
 
The HCP will be asked to complete a brief survey to assess device ease of use for the participant just treated.
 
Void 2:
 
Participants will be asked to not void and to drink approximately 16 fluid ounces of liquid. When the participant feels the need to void (a second time), the HCP will confirm via bladder scanning procedure that the bladder volume is $\geq 125\text{mL}$. If the volume is determined to be inadequate, the participant will be asked if they can wait to void, drink additional fluids as tolerated and be re-assessed in approximately 30 minutes. If the participant does not feel comfortable waiting to void, they will be allowed to proceed with void 2.
 
Void 2 will be repeated per the Void 1 procedure using the 2nd device assigned per randomization.
 
The participant will complete a brief survey (for the second device sequence) immediately following the void to assess device comfort and will then be discharged from the study.
 
The HCP will complete a brief survey to assess device ease of use for the participant just treated.

Investigational Sites	1 site in the US
Data Monitoring Committee	Not Applicable
Regulatory Status	
Post-Market
 
The investigation will use both the PureWick™ Male External Catheter and Sage PrimoFit™ for its intended purpose.

1.2 Schema

2 INTRODUCTION

The PureWick™ MEC is intended for non-invasive urine output management in male patients. The PureWick™ MEC is a single use nonsterile device. It is composed of the following elements: a flexible polyurethane shell, a patient-contacting adhesive intended for up to 24 hours of wear, a spacer fabric layer to function as a fluid pathway, a drainage fitting to connect to standard hospital suction, and vents to allow for air intake. To capture voided urine, the catheter is connected to a wall vacuum system. This vacuum (not felt by the user) is intended to pull urine through the catheter, regardless of the urine flow rate. Urine continues quickly through vinyl tubing until it reaches a collection canister, away from the body.

The PureWick™ MEC does not require a doctor's order, is a commercially available and marketed device commonly used in the hospital setting, and is an FDA 510(k) Exempt, Class I device. See [Appendix 1](#) for the Instructions for Use (IFU).

2.1 Background

Urinary incontinence increases the risk for complications such as incontinence-associated dermatitis (IAD) and pressure ulcers¹⁻⁴, and treatment can be difficult, time-consuming, and costly⁴. Prolonged usage of an indwelling Foley catheter is a well-known risk factor for the development of catheter-associated urinary tract infections (CAUTI). The consequences of urinary tract infections (UTIs) can be serious as they have been found to increase mortality^{5,6}, prolong hospitalization, and increase readmissions⁵. UTIs are a leading cause of the development of bloodstream infections (BSIs) and sepsis, and the most severe infections are associated with increased morbidity, mortality, and costs.⁶

As a result, hospitals are going to great lengths to limit indwelling catheter utilization and minimize the duration of catheterization when it must be used. However, managing urine output without an indwelling catheter has been challenging given the limited device options recently available.

For male patients, condom catheters are an option for external drainage that may allow for accurate urine output measurements and/or management of urinary incontinence. However, there are several disadvantages and challenges associated with sheath-style condom catheter types of devices. First, appropriate sizing of condom catheters may be difficult; too large catheters may simply slip off the penis while too small catheters may cause pressure-associated tissue trauma.⁷ Second, adhesives used to hold the catheter

sheath in place may fail; too little adhesion causes sheath slippage while too strong adhesion may lead to skin damage when the sheath is removed.⁷ Lastly, condom catheters can only be used for males with normal anatomy and cannot be used with men with buried/hidden penis. “A buried penis refers to a normal-sized phallus encompassed by either skin, subcutaneous tissue, and/or fat in the prepubic area” causing a reduced visible and/or functional length of the phallus¹¹; buried penis is an acquired deformity secondary to obesity^{8,9}. Obesity is increasing in our society, with a prevalence of up to 40.8% in middle-aged men.⁸ This condition is also commonly seen in the acute care setting in critically ill patients with third spacing and generalized gross edema. Although no published data are available that could be found regarding the specific incidence of the hidden penis in morbidly obese men, acquired buried penis is increasing in incidence in adult men as morbid obesity becomes more prevalent.¹⁰

The PureWick™ Male External Catheter (MEC) is a new external drainage device to address the need for an effective, non-invasive method of managing urine output in male patients.

2.2 Rationale

The purpose of this study is to provide clinical evidence to compare the effectiveness and comfort of PureWick™ Male against a comparator for non-invasive urine output management in patients with varying male anatomy. Specifically, the study will collect data about how the male external catheters perform when participants are positioned on their side using a turning wedge with the head of the bed elevated, mimicking common patient positioning in the hospital setting.

2.3 Risk/Benefit Assessment

Participants in this study will be treated with approved, marketed devices and will use the investigational devices as intended. Therefore, participants will be exposed to the same risks shared by all patients using these devices for urine output management in a real-world setting. More detailed information about the known and expected benefits and risks and reasonably expected adverse events of the PureWick™ MEC and the Sage PrimoFit™ may be found in the Instructions for Use of each product.

2.3.1 Risk Assessment

Potential Risk of Clinical Significance	Summary of Data/Rationale for Risk	Mitigation Strategy
Study Intervention: PureWick™ Male External Catheter		
Potential adverse events: 
 • Skin injury • Skin irritation • Allergic reaction 	PureWick™ MEC is an external device placed around the base of the penis and adhered to the pelvic skin.	
 • To avoid potential skin injury, never pull the device directly away from the patient. Always peel in the direction from head to foot. • Perform perineal care using the included wipes and assess skin integrity before device application. • Assess the device placement and patient's skin at least every 2 hours. • Monitor for pulling and tension on the device after turning the patient. • Replace the device every 24 hours or if soiled with feces, blood, or semen. • Remove the device prior to ambulation.
Study Intervention: Sage PrimoFit™		
Potential adverse events: 
 • Skin injury • Skin irritation 	Sage PrimoFit™ is an external urine management device for the male anatomy that adheres to the pelvic and abdominal skin.	
 • Clean, prep, and dry patient's genital area before device application • Perform skin assessment every 2 hours

Potential Risk of Clinical Significance	Summary of Data/Rationale for Risk	Mitigation Strategy
		
 Assess device periodically to ensure proper placement, particularly after turning or repositioning patient. Device can be left on skin for up to 24 hours. Replace device if soiled with stool or bodily fluids other than urine. Discontinue use during patient ambulation.
Study Procedures		
Discomfort due to full bladder	Participants will be asked to refrain from voiding until bladder volume reaches $\geq 125\text{mL}$ to ensure a full second void.	
 Participants who meet the eligibility criteria and follow study instructions should not have a bladder that is uncomfortably full.

2.3.2 Benefit Assessment

This is a healthy volunteer study in which the participants are not known to suffer from any of the conditions/indications for use of the PureWick™ MEC or Sage PrimoFit™. As such, there is likely to be no direct benefit for study participants. Data gathered through this study could benefit future patients utilizing the study devices. Study participants may contribute to the process of generating clinical evidence for urine output management in male patients.

2.3.3 Overall Benefit: Risk Conclusion

Taking into consideration the measures to minimize risk to participants in this study, the potential risks identified in association with both the PureWick™ Male External Catheter and the Sage PrimoFit™ are minimal. Both products are commercially available for use. This is a post-market, non-significant risk study.

3 OBJECTIVES AND ENDPOINTS

Objectives	Endpoints
Primary	

 To assess the performance of the PureWick™ Male (System) against an established comparator (Stryker/ Sage PrimoFit™) 	
 Capture rate following void (captured as % of urine captured by device and collected in canister, measured by weight)
Secondary (With Hypothesis Test)	

 To assess the performance of the PureWick™ Male (System) in patients that are unable to use traditional sheath style condom catheters 	
 Capture rate following void (captured as % of urine captured by device and collected in canister, measured by weight)
Secondary (Without Hypothesis Test)	

 To assess participant comfort after using the MEC 	
 Overall Comfort score on a 5-point Likert scale (brief questionnaire)

 To assess ease of use by HCP in placing and removing the MEC 	
 Ease of use score on a 5-point Likert scale (brief questionnaire)

4 STUDY DESIGN

4.1 Overall Design

In this prospective, post-market, crossover, single-blind, single center healthy volunteer study, healthy males will be randomized 1:1 to a treatment sequence using two devices

(PureWick™ Male External Catheter and Sage PrimoFit™) and followed for 1 day through 2 voids. Approximately 50 participants will be enrolled in this study to obtain 44 evaluable subjects. This study is designed to assess the performance, comfort, and ease of use of the PW Male external catheter.

Prior to arrival, participants will be instructed to consume fluids and to come to the study site with a full bladder. Upon arrival at the site, participants will be consented and screened against inclusion/exclusion criteria. Participants meeting eligibility criteria will be assigned a treatment cohort. Participants will be divided into two cohorts.

- A. Non-morbidly obese men: BMI <40 or;
- B. Morbidly Obese men: BMI ≥40.

Prior to any study activities, participants will be asked to review the Informed Consent Form and will have an opportunity to ask the Principal Investigator (PI) any questions. Participants will be considered enrolled after the PI determines they meet the inclusion criteria and receive a signed copy of the Informed Consent Form.

Participants will be placed in the test area, instructed to undress, and put on a gown. The Health Care Professional (HCP) will complete a visual assessment of the participant's pubic/ genital region to ensure that the participant is trimmed and assess the anatomy. Trimmers can be provided if the participant did not arrive to the site trimmed. The HCP will assess for a buried penis and/or anatomical compatibility with traditional sheath style condom catheters for each participant. "A buried penis refers to a normal-sized phallus encompassed by either skin, subcutaneous tissue, and/or fat in the prepubic area" causing a reduced visible and/or functional length of the phallus.¹¹

Void 1:

The bed in the test area will be set with a pre-weighed absorbent pad and a pre-weighed urine collection canister (with the lid). Once the participant feels the need to void, the Health Care Professional (HCP) will place either the PureWick™ MEC or the Sage PrimoFit™ device (depending on randomized treatment order) according to the device instructions for use (IFU) and confirm the correct placement prior to the voiding episode. The participant will be placed in a semi-fowler position (head of bed elevated approximately 30 degrees) in a hospital bed and turned to one side using a turning wedge prior to the voiding episode. Participants will be monitored for approximately 2 hours from the time of the device application, through one void. The skin needs to be assessed at least every two hours while wearing a MEC. After the void, the pre-weighed absorbent pad and urine collection canister will be weighed (with the lid), and weights documented in the source. The Pure Wick MEC or Sage PrimoFit™ will be removed by the HCP. After removal, the HCP will note any signs of irritation/injury in the perineal area. Any

unresolved erythema (redness), erythema (swelling), bleeding, injury, or rash should be recorded as an Adverse Event. The participant will be asked to complete a brief survey to assess device comfort immediately after the completed void.

The HCP will complete a brief survey to assess device ease of use for the participant just treated.

Void 2:

Participants will be asked to not void and to drink approximately 16 fluid ounces of liquid. When the participant feels the need to void (a second time), the HCP will confirm via bladder scanning procedure that the bladder volume is ≥ 125 mL. If the volume is determined to be inadequate, the participant will be asked to drink fluids as tolerated and re-assessed in approximately 30-60 minutes.

Void 2 will be repeated per the Void 1 procedure using the 2nd device assigned per randomization.

The participant will be asked to complete a brief survey (for the second device sequence) immediately following the void to assess device comfort and will then be discharged from the study.

The HCP will complete a brief survey to assess device ease of use for the participant just treated.

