6.5.2 Blinding/Masking

Complete study blinding is not feasible due to possible HCP familiarity with the study devices and visual differences between the product packaging. As such, this is a single-blind study in which only participants are blinded to which device is which. The Investigator and Sponsor will know which device the participant is being treated with at any given time.

Blinding procedures will be reviewed at the time of site initiation by a Sponsor representative. During review of the study and the informed consent process with participants, blinding and rationale should be discussed with the participant.

Any communication to the study personnel placing the device as to the randomized treatment sequence should be done in a way as to prevent the participant from overhearing. Devices should be referred to throughout the study period as 'Device A' and 'Device B' rather than the marketed product name.

Participants will remain blinded to treatment order until the study is complete.

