7.5 Test Procedure

1. After enrollment and randomization, the participant will be brought to the testing area and instructed to undress and put on a gown.
 - a. The bed in the test area will be set with clean sheets, a pre-weighed absorbent pad and a pre-weighed urine collection canister.
2. The Health Care Professional (HCP) will complete a visual assessment of the participant's pubic and genital region to ensure that the participant is trimmed and assess the anatomy.
 - a. Unless the participant arrives with their pubic hair pre-trimmed, the participant's pubic hair will be clipped by themselves or a trained professional.
 - b. The HCP will then complete a brief survey to assess for a buried penis and/or anatomical compatibility with traditional sheath style condom catheters for each participant. "A buried penis refers to a normal-sized phallus encompassed by either skin, subcutaneous tissue, and/or fat in the prepubic area" causing a reduced visible and/or functional length of the phallus.¹¹ for each participant.
3. The HCP will place either the PureWick™ MEC or the Sage PrimoFit™ device (depending on randomized sequence) according to the device IFU and confirm the correct placement.
4. The participant will be placed in a semi-fowler position in the hospital bed and turned to one side using a turning wedge. The HCP should reconfirm correct device placement after repositioning.
5. The HCP will ensure the collection cannister and suction tubing are connected to wall suction and the suction is set to a minimum of 40mmHg continuous suction.
6. Once setup is confirmed and the device is placed, the participant will be allowed to spontaneously void. The participant will be monitored for up to 2 hours, through one void.
7. After the void, the pre-weighed absorbent pad and urine collection canister (with lid) will be weighed and the weights will be documented in the source documents.
8. The Pure Wick MEC or Sage PrimoFit™ will be removed by the HCP according to the IFU and discarded.
9. After removal, the HCP will note any signs of irritation/injury in the perineal area.
 - a. Any unresolved erythema (redness), erythema (swelling), bleeding, injury or rash must be recorded as an Adverse Event.

10. The HCP will complete a brief survey to assess device ease of use for the participant just treated.
11. Participant will be asked not to void and to drink approximately 16 ounces of liquid.

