16.3 Appendix 3: Participant Comfort Scale Survey

To be completed by each participant once per device (total of 2 per participant).

Participant Number:		Void # (Void 1 or Void 2)		
Now that you have experienced the use of the device as well as voiding with the device in place, please answer the following questions considering the use of the current male external catheter.				
1. On a scale of 1 to 5 where 1 is very uncomfortable and 5 is very comfortable, how comfortable was the placement of the male external catheter?				
1 Very uncomfortable	2 Uncomfortable	3 Neither comfortable nor uncomfortable	4 Comfortable	5 Very Comfortable
2. On a scale of 1 to 5 where 1 is very uncomfortable and 5 is very comfortable, how comfortable was the device while you were voiding ?				
1 Very uncomfortable	2 Uncomfortable	3 Neither comfortable nor uncomfortable	4 Comfortable	5 Very Comfortable
3. On a scale of 1 to 5 where 1 is very uncomfortable and 5 is very comfortable, how comfortable was the removal of the male external catheter?				
1 Very uncomfortable	2 Uncomfortable	3 Neither comfortable nor uncomfortable	4 Comfortable	5 Very Comfortable
4. On a scale of 1 to 5 where 1 is very unlikely and 5 is very likely, how likely would you be to recommend the male external catheter to one of your loved ones?				
1 Very Unlikely	2 Unlikely	3 Neither Likely nor Unlikely	4 Likely	5 Very Likely

Protocol Number: UCC-23AC022

CONFIDENTIAL

Version:1.0

Date: 16May2023

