16.4 Appendix 4: Professional Ease of Use Questionnaire

To be completed by HCP after each participant void.

HCP:		Void #:		
Now that you have experienced the application and removal of the device for this participant, please answer the following questions using your professional opinion in regard to device ease of use for this specific participant.				
On a scale of 1 to 5 where 1 is very difficult and 5 is very easy, how easy was the placement of the device?				
1 Very difficult	2 Somewhat difficult	3 Average difficulty	4 Somewhat easy	5 Very easy
On a scale of 1 to 5 where 1 is very difficult and 5 is very easy, how easy was the removal of the device?				
1 Very difficult	2 Somewhat difficult	3 Average difficulty	4 Somewhat easy	5 Very easy

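### The unblinded HCP scores ease of placement only after the void, so knowledge of leakage may influence that rating

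*Protocol*

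**What the plan says.** Protocol Section 4.1 closes the description of each void with the HCP's rating: "The HCP will complete a brief survey to assess device ease of use for the participant just treated". Section 7.5 repeats this as step 10. Three steps earlier, at step 7, it says: "After the void, the pre-weighed absorbent pad and urine collection canister (with lid) will be weighed". Removal by the HCP (step 8) and the HCP's look for irritation or injury (step 9) come in between.

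The form in Appendix 4 carries the instruction "To be completed by HCP after each participant void". Its lead-in addresses a rater who has both applied and removed the device. It has two items, each scored 1 to 5: ease of placement and ease of removal. Neither mentions leakage or capture.

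On blinding, Protocol Section 6.5.2 says that participants alone are blinded and adds: "The Investigator and Sponsor will know which device the participant is being treated with at any given time". The HCP, who handles the device, is therefore not blinded either. For ease of use, Section 6.5 names training and device experience as the foreseeable source of bias. It answers with standardised questionnaires, instructional videos and the IFUs.

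The placement item belongs to the endpoint however it is worded. Protocol Section 10.6 and SAP Section 5.2.4 refer to placing the device; Protocol Section 3 refers to placing and removing it. SAP Section 5.2.4 plans descriptive summaries only.

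**The concern.** Placement is over before the participant voids, yet it is rated afterwards by someone who knows which device was used and may know whether it leaked. A rater who has just dealt with a wet pad may mark placement lower than he or she would have done minutes earlier. If the devices differ in capture, which is what the trial sets out to show, part of that difference could reappear as a difference in ease of placement even if the two devices are equally easy to place.

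What is at stake is whether the ease rating is evidence separate from the capture result. Ease of use is one of the study's three stated purposes (Protocol Section 4.1), and Section 4.2 treats scores of 4 or 5 as the more meaningful ones. No test is planned, so the summary scores are all the evidence there will be. They cannot be repaired later: Section 11.3 says data not properly recorded at the time have no alternate source.

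**Working it through.** **The plan's own figure.** The only design calculation concerns capture rate (Protocol Section 10.2, SAP Section 2.4): a two-sided paired t-test at 0.05, n = 44, and a difference of 0.5 SD. The noncentral t with 43 df and noncentrality 0.5 × √44 gives power 0.9000, so the stated 90% reproduces. It has no bearing on ease of use, which has no sample size basis and no test.

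**Order of events in Protocol Section 7.5.**

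| Step | Event | Person named |
|---|---|---|
| 3 | Device placed | HCP |
| 4 | Participant turned; placement reconfirmed | HCP (reconfirmation) |
| 5 | Suction connection and setting ensured | HCP |
| 6 | Void | Monitoring: nobody named |
| 7 | Pad and canister weighed | Nobody named |
| 8 | Device removed | HCP |
| 9 | Skin checked | HCP |
| 10 | Placement and removal rated | HCP |

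Section 4.1 gives the same order from the void to the survey. So:

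1. The act being rated ends by step 5, and the rating is made at step 10.
2. The result of the void exists from step 6 and is measured at step 7.
3. Whoever does the weighing, the HCP is at the bedside for steps 8 and 9, before scoring, and would probably notice a leak.
4. Neither document has placement scored earlier, uses a rater unaware of leakage, or tells the rater to disregard it. The measures in Section 6.5 do not touch this.
5. The removal item cannot be answered before removal, so the timing concern applies to the placement item alone.

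**Size, by assumption only.** The documents give no SD for the Likert scores, no frequency of visible leakage and no correlation between the two. Two illustrations follow, each with no true difference in ease.

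- In Likert points: shift = (drop in placement score after a visible leak) × (difference between devices in the share of voids with visible leakage). With no drop, the shift is 0. With a drop of 0.5 and a difference of 20 percentage points, 0.5 × 0.2 = 0.10. With a drop of 1.0 and a difference of 30 points, 1.0 × 0.3 = 0.30.
- In SD units: take the design difference in capture, 0.5 SD, and let r be the carry-over correlation from capture difference to placement-score difference. Shift = 0.5 × r, in SDs of the paired score difference. The last column is the chance of p < 0.05 if someone ran a paired t-test on 44 pairs; none is planned.

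| r | Shift (SD) | Chance of nominal p < 0.05 |
|---|---|---|
| 0 | 0 | 5% |
| 0.1 | 0.05 | 6% |
| 0.3 | 0.15 | 16% |
| 0.5 | 0.25 | 37% |

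Nothing in the documents selects a row.

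**The case against.** The strongest reply has five parts.

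- **Who watches and who weighs.** A reader might infer that the HCP watches the void and weighs the leak personally. The documents do not say so. Monitoring is in the passive ("The participant will be monitored for up to 2 hours, through one void"), and so is the weighing. This objection stands, and the point must rest on the order of events and on the HCP's presence at removal.
- **Whether the score is in fact biased.** A reader might go on to say that the score is contaminated and re-measures leakage. Nothing shows this. Appendix 4 asks narrowly about placement and removal, and a trained rater may keep them apart from leakage. This stands too: the bias is possible, and zero belongs in the range.
- **Association is not bias.** An awkward placement can itself cause a leak, so a link between the two may be genuine, and rating after use is a defensible usability choice. That is true, but it favours earlier scoring. A score taken before the void preserves a genuine link. A score taken after it cannot separate hard placement that led to a leak from a leak that lowered the score.
- **Small consequence.** Ease of use has no success criterion and lies outside the fixed sequence. This stands and sets the severity.
- **Participant survey.** Appendix 3 also asks about placement after the void ("Now that you have experienced the use of the device as well as voiding with the device in place"), so a reader might extend the point to it. The documents do not support that: the stated objective is comfort after use, the endpoint is overall comfort, and participants are blinded to device.

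**Conclusion.** The point holds as a minor one. An unblinded rater scores placement after the void, the weighing and the removal, and the plan has no safeguard against knowledge of leakage. The rating may therefore be influenced in favour of whichever device leaked less. The size is unknown; the 0 to 0.30 point range rests wholly on assumed values.

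It would be wrong to read this as a threat to the main result. The capture rate comes from weights, the fixed sequence covers only the two capture-rate tests, and ease of use is summarised descriptively. The primary conclusion and type I error are untouched. What is weakened is any statement that easier placement is a finding separate from better capture.

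**What to change.** In Protocol Sections 4.1 and 7.5, have the HCP record the Appendix 4 placement item once placement and suction connection are confirmed, that is, after step 5 and before the void in step 6. Keep the removal item at step 10. Change the Appendix 4 header and lead-in so that the placement item is answered before the void and the removal item after removal. Leave the participant comfort survey as it is.

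The cut-off should be step 5, not step 4. The PrimoFit IFU (Appendix 2) counts attaching the tubing and setting the vacuum among its placement steps, whereas the PureWick IFU (Appendix 1) puts suction under setup. Scoring after step 5 covers the same span of work for both devices.

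The cost is a form opened twice per device, a small eCRF edit, and a few seconds' wait before the void. That wait is worth keeping short, because Section 2.3.1 lists full-bladder discomfort as a risk. The change does not remove bias from knowing the device, which the design accepts. If the timing stays as it is, the report should list it as a limitation of the ease-of-use result.
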